Experimental Studies of Cigarette Graphic Warning Labels: Analysis Plan

1. Respondent Universe and Sampling Methods

The respondent universe for this study is (1) adolescent current cigarette smokers aged 13-17 years old; (2) adolescents who are susceptible to initiation of cigarette smoking aged 13-17 years old; (3) young adult current cigarette smokers aged 18 to 24 years old; (4) young adult nonsmokers aged 18 to 24 years old; (5) older adult current cigarette smokers aged 25 years old and older; and (6) older adult nonsmokers aged 25 years old and older.

Study participants will be recruited from a national online panel of adults managed by Lightspeed. The Lightspeed panel is a non-probability convenience sample recruited via social media, online recruitment (e.g. via banner placements), and affiliate corporate networks. For the current study, Lightspeed will recruit adult panelists and parents of potential youth respondents using information from panelist's user profiles related to study eligibility (i.e. age, smoking status, and whether or not the panelist has a child in the eligible age range).

Lightspeed panel members will receive an email inviting them to participate in the study. Adolescent children of adult panel participants will be invited to complete the survey through an email invitation to their parents asking for their consent to solicit their child's opinions. Panel members and children of panelists who choose to participate will complete the questionnaire. During the study recruitment, we will monitor the sample and can adjust recruitment targeting as needed to ensure the sociodemographic distribution is diverse in terms of age, gender, education, and ethnicity/race. We estimate a total of 9,760 respondents will complete the baseline data collection. We will administer two follow-up surveys of baseline survey participants, with estimated retention rates of between 50% - 100% for each follow-up session (Table 1).

[figure not shown]
Table 1. Estimated Sample Sizes, by Sample Group and Study Session

Age Group	Smoking Status	Session		
		1	2	3
Adolescent	Current Smoker	230	115 - 230	58 - 230
Adolescent	Susceptible to Smoking	2,070	1,035 - 2,070	518 - 2,070
Young Adult	Current Smoker	1,330	665 - 1,330	333 - 1,330
Young Adult	Nonsmoker	1,330	665 - 1,330	333 - 1,330
Older Adult	Current Smoker	2,400	1,200 - 2,400	600 - 2,400
Older Adult	Nonsmoker	2,400	1,200 - 2,400	600 - 2,400
Total		9,760	4,880 - 9,760	2,440 - 9,760

2. Study Protocol

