10	GHW	WARNING: Smoking causes COPD, a lung disease that can be fatal. [IMAGE 1: BRAIN]	113	131	236	480
11	GHW	WARNING: Smoking causes COPD, a lung disease that can be fatal. [IMAGE 2: MAN]	113	131	236	480
12	GHW	WARNING: Smoking reduces blood flow, which can cause erectile dysfunction.	113	131	236	480
13	GHW	WARNING: Smoking reduces blood flow to the limbs, which can require amputation.	113	131	236	480
14	GHW	WARNING: Smoking causes type 2 diabetes, which raises blood sugar.	113	131	236	480
15	GHW	WARNING: Smoking causes age-related macular degeneration, which can lead to blindness.	113	131	236	480
16	GHW	WARNING: Smoking causes cataracts, which can lead to blindness.	113	131	236	480
TOTAL			2,300	2,660	4,800	9,760

NOTE: SG = Surgeon General's Warning; GHW = Graphic Health Warning

3. Power Analysis

We conducted power calculations to confirm that the overall sample size (shown in Table 2) is sufficiently powered and to determine the optimal sample size and allocation of sample across study conditions. To control for Type 1 error taking into account multiple testing, power calculations were based on the false discovery rate (FDR) (Benjamini & Hochberg, 1995).

Assuming the tests are independent, the FDR is the expected proportion of significant results that are falsely declared as statistically significant. Controlling the FDR is controlling the expected proportion of falsely declared differences (i.e., false discoveries). Controlling the FDR is a more powerful method for dealing with multiple comparisons than other methods that control the family-wise error rate (Benjamini & Hochberg, 1995).

For the overall study sample size, we calculated power to detect a difference in the change in a tobacco-related belief from Session 1 to Session 2 between treatment and control groups (i.e., difference in difference) (Table 3 provides power estimates for Session 2 across various scenarios). RTI calculated power to detect a 0.3 difference on a 7-point scale (two-sided tests, assuming a standard deviation of 1) under different scenarios with variation in FDR, within-person correlation between Session 1 and 2, and sample allocation. RTI conservatively assumed 50% retention from Session 1 to Session 2. Power calculations were computed using 100 simulations for each sample allocation in SAS v9.4.

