For each treatment versus control comparison, will test hypotheses of the following general form:

- H_0 : Average pre-post difference in belief score for those in the treatment condition = average pre-post difference in belief score in the control condition
- H_a : Average pre-post difference in belief score for those in the treatment condition \neq average pre-post difference in belief score in the control condition

To test the hypotheses for Phase 2 analyses, for each outcome we will estimate a regression model of the following general form:

$$\text{Belief} = f(\text{Condition}, \text{Session}, \text{Condition}*\text{Session}, \text{Age}, \text{Smoking Status})$$

where Belief is a measure of agreement with a statement (or set of statements) about the health effects of cigarette smoking, Condition is a dichotomous indicator for a treatment versus control condition, Session is a dichotomous indicator for Session 2 versus Session 1, Condition*Session is the interaction between study condition and study session, Age is a categorical variable for age group (i.e. youth aged 13-17; young adults aged 18-24; and adults aged 25+), and Smoking Status is an indicator for current smoking versus not current smoking (in the adult and young adult samples non-current smokers are never smokers and in the youth sample non-current smokers are those youth susceptible to smoking). These models will include covariates for age and smoking status group to account for potential associations between age, smoking status and outcomes of interest. The key variable of interest in these models is the interaction term, Condition*Session. The coefficient on Condition*Session indicates whether the pre-post change in belief was greater among respondents exposed to a GHW as compared to those exposed to a SG warning. This general model will be repeated for each of 16 treatment versus control group comparisons.

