For those statements which have multiple corresponding belief items that can be scaled into a single continuous variable, we will test these hypotheses using linear regression. For statements with single ordinal Likert-type belief items or for which multiple items are not scalable, we are testing hypotheses of the form that treatment (being exposed to GHW) is associated with a greater pre-post change in level of the ordinal dependent variable than being in the control group (being exposed to an SG warning). Thus, for these items we will use ordinal logistic regression. All regressions, both logistic and linear will be estimated in Stata version 14.1 and will be estimated using Stata's robust standard errors.

In the cases where the dependent variable is continuous and a linear regression model is estimated, the interaction term (Session*Condition) represents the difference in difference of the means or treatment effect. However, in a non-linear model, such as when the dependent variable is ordered and we estimate an ordinal regression model, the coefficient of the interaction term is not a direct measure of the treatment effect due to the non-linear model. As noted in Puhani (2012), in a non-linear model with a strictly monotonic transformation function of a linear index, the sign of the coefficient of the interaction term is equal to the sign of the treatment effect. Testing the significance of the interaction term in the non-linear model is best done via bootstrapping (Puhani, 2012).

As a supplement to the analyses above, we will conduct parallel analyses stratified by age group (i.e. youth aged 13-17; young adults aged 18-24; and adults aged 25+) and smoking status (current smoker versus non-smoker), to examine potential effects within each age and smoking status group. Of note is that this study is not sufficiently powered to detect within-age or

smoking status group differences, and so results from the stratified analyses should be interpreted with caution (i.e., a non-significant finding within an age or smoking status group may reflect lack of statistical power).

A total of 16 statistical tests will be conducted in Phase 2 (not including supplemental age-stratified analyses). To account for the possibility of falsely detecting a significant result (i.e. Type 1 error) arising from multiple statistical tests, we will control for the False Discovery Rate (FDR) using the Benjamini-Hochberg procedure (assuming a two-tailed test and FDR of 0.05).

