We expect some level of overall attrition between Session 1 and Sessions 2 and 3. Although unlikely given the nature of the experimental procedure, there is a potential that the rate of attrition could vary between treatment and control groups, resulting in biased estimates of the effect of the GHWs. To assess potential problems resulting from differential attrition, we will calculate and report rates of overall attrition (i.e., the proportion of Session 1 participants randomly assigned to a treatment or control group for whom Session 2 / Session 3 data are not available) and differential attrition (i.e., the difference in attrition rates between treatment and control groups). We will report overall and differential rates of attrition for each of 16 treatment groups, assessed at Session 2 and Session 3. We have no *a priori* threshold for determining an acceptable level of attrition bias. Nevertheless, to contextualize findings, we can compare attrition rates to benchmarks for randomized controlled trials established by the Department of Education’s What Works Clearinghouse (Deke et al., 2015).

We do not anticipate substantial item non-response, nor do we expect that patterns of item non-response would vary significantly among study conditions. Thus, we will plan to use pairwise deletion to include all available data for each particular analysis. We will examine the data for issues of item non-response and differential item non-response and adjust our approach for handling missing data accordingly.

Model 2: Change in Beliefs at Session 3

To determine the GHW’s sustained impact on targeted beliefs, we will conduct parallel analyses to the Model 1 analyses described above, but with a Session indicator variable that indicates Session 3 versus Session 1 (as opposed to Session 2 vs. Session 1). The general form of this analysis approach is as follows:

$$(\text{Belief}^T_{S3} - \text{Belief}^T_{S1}) - (\text{Belief}^C_{S3} - \text{Belief}^C_{S1})$$

where belief represents the average value (for continuous variables) or probability of being in a higher response category (for ordinally-treated variables), among those in a Treatment (*T*) or Control (*C*) group, at Session 3 (*S3*) or Session 1 (*S1*).

The specific functional form of these models, hypothesis tests, and interpretation of coefficients are identical to those described for Model 1, with the exception that with Model 2 we are examining differences in Session 3 versus Session 1 belief values.

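### Phase 2 treats Session 1 belief as an outcome row, not a baseline covariate: the test is valid but less precise, and open to bias if return depends on baseline belief differently by arm

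*SAP*

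**What the plan says.** Section 2 of the SAP places the first belief assessment before assignment and exposure. Section 4.2 (Model 1) then regresses belief on Condition, Session, their interaction, Age and Smoking Status. In that model "Session is a dichotomous indicator for Session 2 versus Session 1", so each respondent can contribute a Session 1 row and a Session 2 row. The tested term is stated: "The key variable of interest in these models is the interaction term, Condition*Session". On covariates: "These models will include covariates for age and smoking status group to account for potential associations between age, smoking status and outcomes of interest". Session 1 belief is not among them. Model 2 repeats the same form for Session 3 against Session 1.

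Errors "will be estimated using Stata's robust standard errors"; clustering on respondent is not mentioned. On missing answers, "we will plan to use pairwise deletion to include all available data for each particular analysis". On attrition, section 4.2 accepts that a difference between arms could bias the estimates. It plans to report overall and differential rates, with no threshold and no analytic adjustment. Section 1 expects follow-up "with estimated retention rates of between 50% - 100% for each follow-up session", so Session 3 may hold a quarter of Session 1 (Table 1: 2,440 of 9,760).

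**The concern.** A belief measured before randomisation is a true baseline. Using it as an outcome row subtracts it with a coefficient of one, whatever the within-person correlation, and so carries baseline noise into the estimate. Regressing follow-up on baseline lets the data set that coefficient and is never less precise in large samples for a continuous outcome.

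The second issue is who enters the model. If all rows are used, the Session 2 answers of those who return are set against the Session 1 answers of everyone randomised. If only completers are used, the change is within person, but the returners in the two arms may start from different baseline levels. In both cases the interaction can be biased when return depends on baseline belief differently by arm. At stake are the precision of the belief results, mainly at Session 3, and their robustness to attrition that the plan allows to be heavy.

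**Working it through.** **Inputs.** Section 3 "calculated power to detect a 0.3 difference on a 7-point scale (two-sided tests, assuming a standard deviation of 1". Session 1 sizes are 2,080 control and 480 per treatment arm (section 3). Retention of 50% gives 1,040/240 at Session 2 (the section 3 assumption). Retention of 25% gives 520/120 at Session 3 (low end of Table 1). Within-person correlation rho is 0 to 0.8 (Table 3). Assumption: the unadjusted power column of Table 3 uses two-sided alpha 0.05.

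**The plan's own figure.** For 880/250 at rho 0, the change-score variance is 2(1 − rho)k with k = 1/250 + 1/880 = 0.005136. The SE is √0.010273 = 0.1014 and power is Φ(0.3/0.1014 − 1.96) = 0.841. Table 3 states 0.85. The same formula gives all 25 unadjusted cells within the 95% Monte Carlo error of 100 simulations. Table 3 is therefore consistent with a change score in respondents who have both sessions.

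**Three estimators.** With SD 1, k = 1/nT + 1/nC at follow-up and k1 = 1/480 + 1/2,080 = 0.002564:
- all-rows interaction: k + k1 − 2·rho·k1
- completer change: 2(1 − rho)k
- adjusted for Session 1 belief: (1 − rho²)k

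At Session 2, k = 1/240 + 1/1,040 = 0.005128. At rho 0.4 the variances are 0.005641, 0.006154 and 0.004308. At Session 3, k = 1/120 + 1/520 = 0.010256, and at rho 0.4 they are 0.010769, 0.012308 and 0.008615.

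| rho | Adjusted / completer variance | Adjusted / all-rows variance, Session 2 | Session 2 power: all rows / completer / adjusted | Session 3 power: all rows / completer / adjusted |
|---|---|---|---|---|
| 0 | 0.50 | 0.67 | 0.928 / 0.842 / 0.987 | 0.755 / 0.554 / 0.842 |
| 0.2 | 0.60 | 0.74 | 0.957 / 0.912 / 0.990 | 0.789 / 0.649 / 0.856 |
| 0.4 | 0.70 | 0.76 | 0.979 / 0.969 / 0.995 | 0.824 / 0.772 / 0.898 |
| 0.6 | 0.80 | 0.71 | 0.993 / 0.997 / 0.999 | 0.860 / 0.912 / 0.959 |
| 0.8 | 0.90 | 0.51 | 0.999 / 1.000 / 1.000 | 0.895 / 0.997 / 0.999 |

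Power is for a 0.3 difference at alpha 0.05, before the false discovery rate step.

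**Attrition.** The following is an assumption, not in the SAP: the true effect is 0, 50% return in both arms, and return rises with Session 1 belief (log-odds 0.5 per SD) in the graphic-warning arm only. The returners in that arm then have a baseline mean about d = 0.236 SD above the arm's average.
- All rows: bias rho·d = +0.09 at rho 0.4, +0.14 at rho 0.6.
- Completer change: bias −(1 − rho)d = −0.14 at rho 0.4, −0.09 at rho 0.6.
- Adjusted: about 0.

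Attrition rates are equal in this scenario, so a comparison of rates would show nothing. If return depends on baseline equally in both arms, all three are about unbiased.

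If return depends instead on the follow-up belief (same log-odds, one arm, rho 0.6), the biases are 0.24 for all rows, 0.6·0 + 0.4·0.236 = 0.09 for completer change, and (1 − 0.36)·0.236 = 0.15 for the adjusted estimate.

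**The case against.** The plan is coherent: its hypothesis is about pre-post differences, its model tests exactly that, and its power section uses the same contrast. A reader might infer from the missing baseline covariate that the Phase 2 test is invalid. It is not; under randomisation without attrition the interaction estimates the right quantity. Nor is the model wholly unadjusted, since age group and smoking status are in it.

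A reader might also infer a large power loss at Session 2. The SAP's own difference does not support that. Against all rows the gain is about 6 points at rho 0 and under 2 points at rho 0.4 and above. A larger gain appears for a difference of 0.2, but the SAP does not plan for 0.2.

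Nor is it settled that all rows will be used. The sentence on all available data concerns item non-response, the plan says it may change its handling of missing data after inspecting it, and Table 3 fits a completer change score. What stands is that the row set is not stated, and that both readings are less precise than adjustment.

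The bias figures rest on an assumed mechanism, and the SAP considers differential attrition unlikely. That is fair. Adjustment is no general cure either: when drop-out follows later belief, it can be worse than completer change. Finally, the variance ratios apply to continuous outcomes. Analyses 1 to 5 and 8 are ordinal for certain, and others may become so.

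**Conclusion.** The point holds as one of efficiency and robustness. For a continuous outcome with SD 1, adjusting for Session 1 belief has lower variance at every Table 3 correlation, whichever rows are used, and needs no new data. The power benefit is small at Session 2 and material at Session 3 with 25% retention: 7 to 10 points over all rows, depending on rho.

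The possible bias is about a third to a half of the 0.3 target (0.09/0.3 = 0.31; 0.14/0.3 = 0.47). It requires drop-out related to baseline belief and differing by arm, which is an assumption. The documents do not show that such drop-out will occur, and a reader should not infer that the planned results will be biased. They do leave open which rows enter, and that choice alone reverses the sign of the bias in this scenario. The sizes do not carry over directly to the ordinal models.

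**What to change.** Make the Phase 2 test: Session 2 (or Session 3) belief = f(Condition, Session 1 belief, Age, Smoking Status), with one row per respondent who has follow-up data, and robust errors. Use linear regression for scales, and ordinal logistic regression with the Session 1 response as a categorical covariate for single items. Keep the difference-in-difference means as a descriptive table. One row per respondent also removes the question of clustering and the need to interpret an interaction in a non-linear model, which section 4.2 itself flags. Add a sensitivity analysis for drop-out that depends on later belief, because adjustment does not cover it.

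The cost is a rewrite of one model and of its hypotheses; no data or sample is added. For linear models the target mean effect is unchanged under randomisation. For ordinal models it is not: odds ratios are non-collapsible, so the adjusted odds ratio is conditional on baseline and differs from the interaction odds ratio. Report it as conditional, or give a marginal difference in probabilities.

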Across various assumptions of within-person correlation and FDR, we found generally higher levels of power using an optimized sample allocation with between 1,760 and 2,400 participants assigned to the control condition at Session 1 (880-1,200 participants at Session 2, assuming 50% retention). Based on this analysis showing that higher power is achieved with an unbalanced allocation, FDA plans to allocate 2,080 to the control group and 480 to each treatment group at Session 1.

Table 3. Study Power by Sample Allocation at Session 2

Sample Allocation at Session 2		Within-person Correlation	FDR					Unadjusted Power
Control	Treatment		0.05	0.1	0.15	0.2	0.25	
287	287	0	0.60	0.71	0.83	0.89	0.91	0.68
880	250	0	0.80	0.89	0.94	0.95	0.97	0.85
1,200	230	0	0.77	0.87	0.90	0.94	0.95	0.81
1,520	210	0	0.88	0.92	0.94	0.96	0.98	0.88
1,840	190	0	0.72	0.84	0.88	0.92	0.93	0.78
287	287	0.2	0.64	0.77	0.83	0.89	0.90	0.73
880	250	0.2	0.95	0.95	0.97	0.99	0.99	0.96
1,200	230	0.2	0.89	0.94	0.95	0.98	1.00	0.91

1,520	210	0.2	0.87	0.92	0.94	0.96	0.98	0.89
1,840	190	0.2	0.85	0.88	0.94	0.94	0.99	0.87
287	287	0.4	0.85	0.91	0.96	0.98	0.99	0.89
880	250	0.4	0.97	0.98	0.99	0.99	1.00	0.98
1,200	230	0.4	0.97	1.00	1.00	1.00	1.00	0.97
1,520	210	0.4	0.95	0.97	0.97	0.97	0.98	0.95
1,840	190	0.4	0.91	0.94	0.97	0.97	0.97	0.91
287	287	0.6	0.97	0.98	0.98	1.00	1.00	0.98
880	250	0.6	1.00	1.00	1.00	1.00	1.00	1.00
1,200	230	0.6	1.00	1.00	1.00	1.00	1.00	1.00
1,520	210	0.6	1.00	1.00	1.00	1.00	1.00	1.00
1,840	190	0.6	1.00	1.00	1.00	1.00	1.00	1.00
287	287	0.8	1.00	1.00	1.00	1.00	1.00	1.00
880	250	0.8	1.00	1.00	1.00	1.00	1.00	1.00
1,200	230	0.8	1.00	1.00	1.00	1.00	1.00	1.00
1,520	210	0.8	1.00	1.00	1.00	1.00	1.00	1.00
1,840	190	0.8	1.00	1.00	1.00	1.00	1.00	1.00

Note: FDR = False Discovery Rate

4. Analysis

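### Phase 2 stacks two belief records per participant but specifies plain robust standard errors, so the difference-in-difference tests ignore the pairing and are too conservative

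*SAP*

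**What the plan says.** SAP Section 4.2, Model 1, fits belief as a function of condition, session, condition by session, age group and smoking status. Session is a two-level indicator, so a participant seen at both sessions contributes two records. The test is on the product term: "The key variable of interest in these models is the interaction term, Condition*Session".

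Scaled outcomes get linear regression, and single or unscalable items get ordinal logistic regression. On the error variance the section says "All regressions, both logistic and linear will be estimated in Stata version 14.1 and will be estimated using Stata's robust standard errors". For the ordinal models it adds "Testing the significance of the interaction term in the non-linear model is best done via bootstrapping", without committing to a bootstrap or giving a resampling unit. Model 2 repeats the same form for Session 3 against Session 1.

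Within-person correlation appears only in Section 3, where power was computed with "variation in FDR, within-person correlation between Session 1 and 2, and sample allocation". In Table 3, power rises as that correlation rises.

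**The concern.** Stata's plain robust variance allows for unequal variances but treats every row as independent. Phases 1 and 3 use essentially the same sentence for models with one record per person, where there is nothing to cluster. In Phase 2 the sentence no longer suffices, because the two rows come from the same person answering the same item, one to two days apart in Model 1.

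The interaction compares changes within people, so a positive correlation reduces its true variance. An analysis that ignores the correlation reports standard errors that are too large, intervals that are too wide and p-values that are too high. Linear point estimates are unaffected and false positives are not inflated. The risk is that a warning that does change beliefs is reported as not doing so. This applies to all 16 Model 1 comparisons and their Model 2 counterparts. The power in Table 3 also belongs to a different analysis from the one written down.

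**Working it through.** **Inputs (SAP Section 3 and Tables 2 and 3).** Difference in difference 0.3, SD 1 per session, two-sided tests, rho from 0 to 0.8. Allocation: "FDA plans to allocate 2,080 to the control group and 480 to each treatment group at Session 1". Retention: "RTI conservatively assumed 50% retention from Session 1 to Session 2". This gives nC = 2,080 × 0.5 = 1,040 and nT = 480 × 0.5 = 240 at Session 2.

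**Formulas for complete pairs (sigma = 1).**
- True variance of the interaction: 2(1-rho)(1/nT + 1/nC).
- Variance reported when rows are treated as independent: 2(1/nT + 1/nC).
- Power with the correct SE: Φ(δ/SE_true − z).
- Power with the plain SE: Φ((δ − z·SE_plain)/SE_true).
- True type I error with the plain SE: 2[1 − Φ(z·SE_plain/SE_true)].

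**Reproducing Table 3.** Take 1,200 control and 230 treated at rho 0.4.
- Paired: SE = sqrt(1.2 × (1/1,200 + 1/230)) = 0.0789, and power = Φ(0.3/0.0789 − 1.96) = 0.967. The table gives 0.97.
- Unpaired: SE = sqrt(2 × (1/1,200 + 1/230)) = 0.1018, and power is 0.838.

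Over the 25 unadjusted-power rows, the paired formula agrees within 2 points in 19. The other six lie within about 2.1 Monte Carlo standard errors, given 100 simulations. A fully unpaired calculation gives the same power at every rho, so it cannot produce the rise in the table. Table 3 therefore rests on a paired analysis.

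**Planned size, complete pairs.** The plain SE is sqrt(2 × (1/1,040 + 1/240)) = 0.101 at every rho.

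| rho | correct SE | inflation | true error at nominal 0.05 | power for 0.3 at 0.05: plain / correct | power for 0.3 at 0.05/16: plain / correct |
|---|---|---|---|---|---|
| 0 | 0.101 | 1.00 | 0.050 | 0.84 / 0.84 | 0.50 / 0.50 |
| 0.2 | 0.091 | 1.12 | 0.028 | 0.87 / 0.91 | 0.50 / 0.64 |
| 0.4 | 0.078 | 1.29 | 0.011 | 0.90 / 0.97 | 0.50 / 0.81 |
| 0.6 | 0.064 | 1.58 | 0.002 | 0.94 / 0.997 | 0.50 / 0.96 |
| 0.8 | 0.045 | 2.24 | <0.001 | 0.99 / 1.00 | 0.51 / 1.00 |

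The last column uses the strictest Benjamini-Hochberg step for 16 tests, 0.05/16 = 0.0031 (z = 2.955). For a 0.2 difference at rho 0.6 and unadjusted 0.05, power is 0.51 plain against 0.88 correct.

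**All available rows, 50% retention.** Session 1 has n per arm and Session 2 has n/2. The covariance of the two session means is rho/n, so the true variance is (3 − 2·rho)(1/2,080 + 1/480), while the plain variance is 3(1/2,080 + 1/480). This assumes drop-out unrelated to belief. Inflation is sqrt(3/(3 − 2·rho)): 1.07, 1.17, 1.29 and 1.46 at rho 0.2 to 0.8. At rho 0.6 the SEs are 0.088 plain and 0.068 correct:
- power for 0.3 at 0.05: 0.97 against 0.99;
- power for 0.3 at 0.05/16: 0.73 against 0.93;
- power for 0.2 at 0.05: 0.66 against 0.84.

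**Simulation at rho 0.6** (1,000 linear runs per setting with age and smoking covariates; 150 ordinal runs without covariates).

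| Setting | empirical SE | plain robust SE | clustered SE | null rejection: plain / clustered |
|---|---|---|---|---|
| Linear, complete pairs | 0.065 | 0.101 | 0.064 | 0.3% / 5.1% |
| Linear, all rows, 50% attrition | 0.068 | 0.088 | 0.068 | 1.0% / 4.6% |
| Ordinal logistic | 0.122 | 0.182 | 0.122 | not computed |

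The clustered error matches the empirical one in each case, and the plain robust error does not.

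**The case against.** The SAP never says that rows are independent. It gives only a general model form, calls Phase 2 longitudinal and uses the within-person correlation in its power section, so the analysts may well intend a participant-clustered variance. That is possible. But no cluster variable is named anywhere, and the error sentence is in substance the one used for the single-record phases. A programmer following the text would run the unclustered version.

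The bootstrap remark could rescue the ordinal models, which cover at least the six single-item comparisons (conditions 1 to 5 and 8). If participants were resampled, it would. The remark is better called non-committal than contradictory, since robust errors could be a general setting and the bootstrap a specific test. It still fixes no resampling unit, does not reach the linear models, and leaves open which p-value is used.

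On size, three points stand. The plan to use all available data makes the smaller inflation (1.07 to 1.46) the more natural reading at 50% retention. The largest unadjusted power loss is for a 0.2 effect, whereas the planned effect is 0.3. And 50% is the low end of the retention range: at 75%, plain-robust power for 0.3 at unadjusted 0.05 is at least 0.95 at every rho. These points limit the loss but do not make the standard errors correct.

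**Conclusion.** The concern holds. Followed as written, Section 4.2 gives standard errors, intervals and p-values for every belief comparison that are wrong in the conservative direction whenever the within-person correlation is positive. At the planned size with 50% retention, the SE is too large by a factor of 1.12 to 2.24 for complete pairs, or 1.07 to 1.46 if unpaired Session 1 rows are kept, over rho 0.2 to 0.8.

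For the planned 0.3 effect at unadjusted 0.05, power stays at 0.84 or above. The loss falls mainly on FDR-adjusted tests and on smaller effects. The 0.05/16 figures are the worst case, and the loss is smaller when many of the 16 comparisons succeed.

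The sizes rest on SD 1, equal variance at both sessions and an unknown rho. The SAP considers 0 to 0.8, and at rho 0 there is no error. The closed forms apply to the linear models; the ordinal models are supported by simulation.

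**What to change.** In Section 4.2, for Models 1 and 2, replace the general robust-error statement with one saying that standard errors are clustered on participant, in Stata `vce(cluster id)` with the participant identifier. If the ordinal interaction is to be tested by bootstrap, state that participants, with all their records, are resampled. Name one method, clustered or bootstrap, as the source of the p-value that enters the Benjamini-Hochberg procedure. Say also whether Session 1 records of participants without follow-up stay in the model.

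The cost is one command option and a few SAP sentences. Design, sample size and data collection do not change, and the analysis then matches the paired calculation behind Table 3.
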